9.2.2 Assessment of secondary outcomes

- For the analysis of time to clinical improvement of at least 2 points in the WHO Ordinal Scale for Clinical Improvement, clinical severity will be assessed every day until day 14 according to the Scale with the worst status for that day recorded
- For the analysis of the proportion of patients alive and not having required invasive or non-invasive ventilation at 14 days after enrolment, admission to ICU with invasive or non-invasive ventilation or death will be assessed every day until day 14.
- For the analysis of the proportion of patients with ALI within 14 days after enrolment, PaO₂/FiO₂ will be determined daily until day 14. This is only relevant for patients with arterial blood gas sampling performed in the ICU or rarely on the ward.

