
Measurements and procedures:
	
After providing informed consent a pregnancy test will be performed if appropriate. Only subject who fulfilling all eligibility criteria will be randomised in a 2:1 ratio in an open-label controlled design to treatment with conestat alfa in addition to SOC or SOC only starting on day 0. The first conestat alfa treatment will usually be administered on the same day and continued for a maximum of 64 hours (+/-4 hours).
 
Vital signs, disease severity, clinical improvement, admission to ICU, receipt of additional anti-inflammatory therapies such as tocilizumab and requirement for non-invasive or invasive ventilation will be documented. Disease severity will be evaluated by the WHO Ordinal Scale:
 
  
 Patient State	Description	Score	
   
 Outpatient	No limitation in activities	1	
 
 Limitation in activities	2	
 
 Hospitalized Mild disease	No oxygen therapy	3	
 
 Oxygen by mask or nasal prongs	4	
 
 Hospitalized Severe disease	Non-invasive ventilation or high-flow oxygen	5	
 
 Intubation, mechanical ventilation +/- additional organ support	6	
 
 Death	Death	7	
  
 
Virological clearance will be assessed at 14 days after enrolment or discharge. Routine laboratory parameters and changes in certain biomarker levels will be assessed during 14 days or until discharge.
 
C1INH pharmacokinetics and complement and inflammatory proteins will be assessed (in Basel, optional for other centers) during 14 days or until discharge.
 
Follow-up will include a structured telephone interview or study visit (if still admitted) after 4 weeks to assess adverse events and outcome.
	Patient State	Description	Score	Outpatient	No limitation in activities	1	Limitation in activities	2	Hospitalized Mild disease	No oxygen therapy	3	Oxygen by mask or nasal prongs	4	Hospitalized Severe disease	Non-invasive ventilation or high-flow oxygen	5	Intubation, mechanical ventilation +/- additional organ support	6	Death	Death	7
Patient State	Description	Score																				
Outpatient	No limitation in activities	1																				

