3.8 Justification of choice of study population

Approximately 20% of patients with COVID-19 infection require hospitalization for supportive treatment. The majority of these patients will suffer from viral pneumonia visible on chest CT scans. Approximately 15-20% of these patients will progress to severe ALI requiring mechanical ventilation and ICU support. Patients with confirmed COVID-19 disease and admitted to a non-ICU ward will be eligible for the study. This population was chosen, as anti-inflammatory treatments such as conestat alfa may interfere most effectively during stage II disease, i.e. during the early inflammatory response phase. In addition, interventions that prevent patients from deteriorating and requiring mechanical ventilation are highly desired and represent an area of unmet clinical need in a pandemic situation with limited ICU and ventilation support capacity. This population offers the opportunity to impact not only on an individual but also on a population level.

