5.2 Secondary Outcomes

The secondary endpoints will evaluate the effect of conestat alfa treatment in addition to SOC treatment relative to only SOC treatment on disease progression as measured by

- Time to clinical improvement (time from randomisation to an improvement of two points on the seven-category WHO ordinal scale or live discharge from hospital, whichever came first) within 14 days after enrolment.
- Proportion of participants alive and not having required invasive or non-invasive ventilation at 14 days after enrolment.

- Proportion of subjects with an ALI (defined by PaO₂/FiO₂ ratio of ≤300mmHg) within 14 days after enrolment

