9. STUDY ASSESSMENTS

9.1 Study flow chart(s) / table of study procedures and assessments

Study Periods	Screening	Intervention Period				Follow-up	
		1	2	3	4	5	6
Visit	1	2	3	4	5	6	7
Time (weeks or days, or hours)	d-1 to d0 ¹	d0	d1	d2	d3-13 during admission*	d14 (+/-2d) or discharge	wk4 (+/-5d)
In- /Exclusion Criteria	x						
Patient Information and Informed Consent	x						
Randomisation	x						
Demographics		x					
Medical History and Physical Examination		x				x	
Vital Signs including Respiratory Rate ⁹		x	x	x	x	x	
Laboratory Tests (blood)		x	x		x ³	x	
Virology testing		x ²			x ²	x ²	
Administer Study Medication ⁴		x	x	x	x		
Assessment of WHO ordinal scale		x	x	x	x	x	x
Assessment of ICU admission and/or mechanical ventilation		x	x	x	x	x	x
Laboratory assessment in detail:							
Routine full blood count		x ⁵	x		x ³	x	
Routine coagulation studies		x ⁵	x		x ³	x	
Routine biochemistry including LDH		x ⁵	x		x ³	x	
Serum pregnancy test	x ⁶						
Ferritin, IL-6, D-Dimer		x ⁵	x ¹¹		x ³	x	
C1INH concentration ⁷		x	x			x	
Additional samples in Basel ¹⁰ :		x					
Complement proteins (e.g. C4d, C5a)		x	x		x ³	x	
Inflammatory cytokines (e.g. IL-10)		x	x		x ³	x	
Contact activation and coagulation proteins (e.g. factor XII)		x	x		x ³		
C1INH concentration and activity		x ⁸	x ⁸		x (d3, 7, 10)	x	
Urinary markers of renal injury		x	x		x ³	x	
Blood volume (ml), total/study specific (Basel ¹⁰)	5/5 (5)	12/12 (22)	12/12 (22)		12/5 (10)	12/12 (17)	
Urine volume (ml), study specific in Basel ¹⁰		5	5		5	5	
(Serious) Adverse Events		x	x	x	x	x	x

¹Eligibility criteria have to be assessed within 72 hours after hospital admission. Randomisation may occur on the day of hospital admission.

²Monitoring of SARS-CoV-2 viral load will be performed in Basel and optional in other centers. This will include performance of a quantitative SARS-CoV-2 PCR from upper or lower respiratory tract at baseline

and subsequently once between day 4-7 (according to local standard) and again on day 14 if participants are still admitted or between day 10-13 if discharged earlier. Standard operating procedures include the performance of a second swab following a first negative swab.

³Routine laboratory tests will be performed on days 3, 5, 7, and 10 during hospital admission according to standard procedures of the study site, but will include a set of hematology, coagulation and biochemistry parameters. Additional blood samples will be collected at the same time.

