9.2 Assessments of outcomes

9.2.1 Assessment of primary outcome

For the analysis of the primary endpoint, illness severity will be assessed on each day after enrolment (worst status) with the use of the WHO Ordinal Scale for Clinical Improvement (score 0 will be omitted and score 6 and 7 will be combined) and the score on day 7 will be analysed stratified by its baseline value.

Patient State	Descriptor	Score
Uninfected	No clinical or virological evidence of infection	0
Ambulatory	No limitation of activities	1
	Limitation of activities	2
Hospitalized Mild disease	Hospitalized, no oxygen therapy	3
	Oxygen by mask or nasal prongs	4
Hospitalized Severe Disease	Non-invasive ventilation or high-flow oxygen	5
	Intubation and mechanical ventilation	6
	Ventilation + additional organ support – pressors, RRT, ECMO	7
Dead	Death	8

Figure 4: WHO ordinal scale for clinical improvement. For the current study, score 0 will be omitted, and score 6 and 7 will be combined.

The worst score on a given day (between 0:00 and 24:00 hours) will be used for the categorization

Patient State	Description	Score
---------------	-------------	-------

Outpatient	No limitation in activities	1
	Limitation in activities	2
Hospitalized Mild disease	No oxygen therapy	3
	Oxygen by mask or nasal prongs	4
Hospitalized Severe disease	Non-invasive ventilation or high-flow oxygen	5
	Intubation, mechanical ventilation +/- additional organ support	6
Death	Death	7

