- Only in Basel and in the active treatment group: Collection of blood (5ml) for the analysis of C1INH levels and activity 10 (+/-5 minutes) after the first administration.

Visit 3, Intervention period (Day 1)

- Administration of 4200 U of conestat alfa every 8 hours in the active treatment group as per treatment schedule. The time of dosing and the dose will be recorded.
- Assessment of vital signs including respiratory rate.
- Assessment of WHO ordinal scale and need for oxygen supplementation
- Documentation of ICU admission and/or non-invasive or invasive ventilation
- Collection of blood (12ml) for analysis of ferritin, D-Dimer, C1INH concentration, and in Basel (optional for other centers): collection of blood (5ml) and urine (5ml) for the analysis of complement proteins, parameters of the contact activation and coagulation system, renal injury markers and inflammatory cytokines. Routine full blood count, coagulation and biochemistry studies will only be performed if results from prior tests on the same day are not available.
- Only in Basel and in the active treatment group: Collection of blood (5ml) for analysis of C1INH levels and activity 10 (+/-5 minutes) after any of the three administrations of conestat alfa on that day.

- Assessment of AEs.

Visit 4, Intervention period (Day 2)

- Administration of 4200 U of conestat alfa every 8 hours in the active treatment group as per treatment schedule. The time of dosing and the dose will be recorded.
- Assessment of vital signs including respiratory rate.
- Assessment of WHO ordinal scale and need for oxygen supplementation
- Documentation of ICU admission and/or non-invasive or invasive ventilation
- Assessment of AEs.

Visit 5, Intervention period (Day 3-13 during hospital admission)

- Completion of treatment with conestat alfa (9 administrations in total including the first 8400 U administration) in the active treatment group as per treatment schedule. The time of dosing and the dose will be recorded.
- Assessment of vital signs including respiratory rate.
- Assessment of WHO ordinal scale and need for oxygen supplementation. If the patient was already discharged before day 7, the assessment of the WHO ordinal scale will be conducted via a short telephone interview (Score 1 or 2).
- Documentation of ICU admission and/or non-invasive or invasive ventilation

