- Routine laboratory tests will be performed on days 3, 5, 7 and 10 during admission according to standard procedures, and should include a set of hematology, coagulation and biochemistry parameters. Additionally, blood (5ml) for analysis of ferritin, IL-6, D-Dimer, C1INH concentration will be collected at the same time point, and in Basel (optional for other centers): collection of blood (5ml) and urine (5ml) for the analysis of complement proteins, parameters of the contact activation and coagulation system, renal injury markers and inflammatory cytokines.
- Virological assessment (quantitative SARS-CoV-2 PCR in respiratory specimen) should be performed on day 4-7 (according to local standard). This is optional for all centers except Basel.
- Assessment of AEs

Visit 6, Follow-up (Day 14 (+/-2 days) or at discharge)

- Physical examination including body weight.
- Assessment of vital signs including respiratory rate.
- Assessment of WHO ordinal scale and need for oxygen supplementation
- Documentation of ICU admission and/or non-invasive or invasive ventilation
- Laboratory assessment including routine hematology, coagulation and biochemistry studies (7ml). Routine laboratory tests will be performed every second day during admission according to standard procedures. Additional sample collection will be required in patients without routine testing on the day of discharge. Additionally, blood (5ml) for analysis of ferritin, IL-6, D-Dimer, C1INH concentration will be collected at the same time point, and in Basel (optional for other centers): collection of blood (5ml) and urine (5ml) for the analysis of complement proteins, renal injury markers and inflammatory cytokines.
- Virological assessment (quantitative SARS-CoV-2 PCR in respiratory specimen) will be performed on day 14 (when still admitted) or at discharge if on day 10-13. This is optional for all centers except Basel.
- Assessment of AEs.

Visit 7, Follow-up (week 4 +/- 5 days, telephone interview or study visit if still admitted)

- Assessment of adverse events, WHO ordinal scale, admission to ICU and/or mechanical ventilation by structured telephone interview. If necessary, medical charts will be reviewed, discharge summaries will be obtained or the patients' general practitioner will be contacted regarding specific follow-up information.

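### Section 9.2.2 ties ventilation to ICU admission when assessing the ventilation-free survival endpoint, which is narrower than the endpoint's own definition

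*Protocol*

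**What the plan says.** Section 5.2 of the protocol defines the endpoint as "Proportion of participants alive and not having required invasive or non-invasive ventilation at 14 days after enrolment". Section 4.3, the synopsis and section 11.4.3 give the same definition. None of them mentions the ICU. Section 11.4.3 places the endpoint among those tested once the primary test is significant. The synopsis paragraph on statistics names only time to improvement in that role.

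Section 9.2.2 restates the endpoint and then says what is assessed for its analysis: "admission to ICU with invasive or non-invasive ventilation or death will be assessed every day until day 14".

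Other sections bear on how ventilation is recorded:

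- Section 9.3.1, Visits 3 to 6: "Documentation of ICU admission and/or non-invasive or invasive ventilation".
- Synopsis, measurements and procedures: "admission to ICU, receipt of additional anti-inflammatory therapies such as tocilizumab and requirement for non-invasive or invasive ventilation will be documented".
- Schedule in section 9.1: "Assessment of ICU admission and/or mechanical ventilation".
- Section 9.3.1, Visit 7 at week 4: "admission to ICU and/or mechanical ventilation by structured telephone interview".
- Section 9.2.1, description of WHO score 5: "Non-invasive ventilation or high-flow oxygen".

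**The concern.** The endpoint has a definition and an assessment rule, and they do not cover the same events. The definition turns on whether the patient needed ventilation. The rule, read literally, turns on ventilation together with ICU admission. An analyst who follows 9.2.2 and one who follows 5.2 could classify the same patient differently.

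The difference matters because placement in an ICU is a separate decision from the need for ventilation. It can depend on beds and local practice, and section 6.1 plans sites in three countries. Section 3.8 refers to "limited ICU and ventilation support capacity" as part of the reason for choosing this population. Section 6.2.2 leaves patients, physicians and investigators unblinded, and section 6.2 relies on objective endpoints, besides randomisation, to limit bias. An endpoint that needs ICU admission is less objective than one that asks only whether ventilation was given.

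**Working it through.** **No stated figure to reproduce.** The protocol gives no event rate, effect size or power for this endpoint. The main check is a comparison of texts.

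**Step 1: classify patient courses up to day 14 under each wording.**

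| Course to day 14 | Definition (4.3, 5.2, 11.4.3) | Literal 9.2.2 |
|---|---|---|
| Death | Failure | Failure |
| Ventilation of either kind in an ICU | Failure | Failure |
| Survivor, non-invasive ventilation outside an ICU only | Failure | No failure event |
| Survivor, high-flow oxygen only | Not stated | Not stated |
| Survivor, neither | Success | Success |

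The two wordings part on the third row. The fourth row is open under both.

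**Step 2: is the ICU condition only loose wording?** Elsewhere the protocol keeps ICU admission and ventilation apart. Section 7.1 has separate exclusion criteria for them. Section 5.3 lists ICU treatment and mechanical ventilation as separate outcomes. Visits 3 to 6 join them with and/or, where 9.2.2 uses with. The next item of 9.2.2, on acute lung injury, distinguishes the ICU from the ward. The sentence may still simply presume that ventilation takes place in an ICU, but it does not say so.

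**Step 3: can other data settle the third row?**

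- The visit record can. Visits 3 to 6 document non-invasive ventilation with or without ICU admission.
- The WHO score alone cannot, because score 5 pools non-invasive ventilation with high-flow oxygen.
- For a patient discharged before day 14, Visit 6 takes place at discharge and covers the stay up to then. The remaining gap is a readmission before day 14 with non-invasive ventilation outside an ICU. The week-4 interview does not name that event.

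**Step 4: illustration of size, on assumptions.** Let *f* be the share of all failures that are survivors with non-invasive ventilation outside an ICU only. The protocol gives no value, so *f* runs from 0 to 50%. Control failure is set at 15% or 20%, borrowed from section 3.8 as a scale only. That figure describes patients who progress to mechanical ventilation with ICU support, so it is not a rate of the cases at issue. Treatment is assumed to halve failure. Arm sizes are 40 and 80 (section 6.1).

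Observed risks are p(1 − f) in each arm. With observed risks p₁ (control) and p₂ (treated), d = p₁ − p₂ and p̄ = (40p₁ + 80p₂)/120:

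- SE₀ = √[p̄(1 − p̄)(1/40 + 1/80)]
- SE₁ = √[p₁(1 − p₁)/40 + p₂(1 − p₂)/80]
- power = Φ[(d − 1.96·SE₀)/SE₁]

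For 20% v 10% and f = 0: p̄ = 16/120 = 0.133, SE₀ = 0.0658, SE₁ = 0.0716, and power = Φ[(0.10 − 0.129)/0.0716] = Φ(−0.41) = 34%.

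| True risks | f | Expected failures not counted | Observed risks | Power |
|---|---|---|---|---|
| 20% v 10% (8 + 8 = 16 failures) | 0 | 0 | 20% v 10% | 34% |
| | 25% | 4 | 15% v 7.5% | 27% |
| | 50% | 8 | 10% v 5% | 20% |
| 15% v 7.5% (6 + 6 = 12 failures) | 0 | 0 | 15% v 7.5% | 27% |
| | 25% | 3 | 11.25% v 5.6% | 22% |
| | 50% | 6 | 7.5% v 3.75% | 17% |

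The same *f* is used in both arms, so the table says nothing about a difference between arms.

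**The case against.** The best reply is that nothing is misclassified. The endpoint is defined several times without an ICU condition, and the 9.2.2 sentence itself opens by repeating that definition. It then lists what is looked at each day and sets no coding rule. The information needed is collected at Visits 3 to 6, and section 9.2.3 separately records ICU dates and mechanical-ventilation dates. For events after discharge, Visit 7 allows chart review and discharge summaries, section 9.2.4.1 asks participants to report new admissions, and section 10.1.1 makes a hospital admission a serious adverse event. The endpoint is secondary, in an exploratory pilot, and is tested only after a significant primary result.

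Much of this stands, and it rules out several stronger readings that a reader might infer:

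- *That the protocol counts ward ventilation as success.* No section says so; the literal wording only permits it.
- *That failures go unrecorded.* The visit record captures them, apart from the narrow period after discharge.
- *That a definite number of patients would be misclassified.* Any such number needs an assumed share, which may be zero.
- *That the arms would be affected differently.* The open-label design makes this possible, but nothing in the protocol shows it.
- *That high-flow oxygen is plainly not a failure.* The exclusion criterion in section 7.1 needed an explicit exception for it, and the endpoint carries none.

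What does not stand is that the mismatch is harmless because the data exist. Having the data does not tell the analyst which wording governs. Nor is this a detail left to the statistical analysis plan: the protocol states how the endpoint is assessed, and that statement disagrees with its own definition.

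**Conclusion.** The point holds as an internal inconsistency. Section 9.2.2 assesses a narrower event than sections 4.3, 5.2 and 11.4.3 define, and narrower than Visits 3 to 6 record. Under its literal wording, a survivor given non-invasive ventilation only outside an ICU could be classed as a success although the definition makes that patient a failure.

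The size is unknown. The illustration gives 0 to 8 uncounted failures and a loss of 0 to 14 percentage points of power that is already low, on assumed failure risks, an assumed halving on treatment and an assumed share of 0 to 50%. These figures show how the effect would scale; they are not estimates for this trial. The point is worth correcting because section 11.4.3 makes this a tested endpoint and the remedy is small. It does not touch the primary analysis.

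**What to change.** Reword the second item of 9.2.2 so that the assessed event is *death or any invasive or non-invasive ventilation, in any hospital unit, from randomisation to day 14*, and state that it is derived from the ventilation documentation made at Visits 3 to 6.

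Add a sentence saying whether high-flow oxygen alone counts towards this endpoint. WHO score 5 cannot separate it from non-invasive ventilation, and the sentence should be consistent with the exception in the exclusion criterion of section 7.1.

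In the week-4 interview, name non-invasive ventilation and record its date, to cover readmission before day 14.

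The cost is two sentences in the protocol and one item on the telephone form. The inpatient data are already collected, and the change concerns outcome classification only, not patient care.

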9.2.3 Assessment of other outcomes of interest

- The following assessments will be performed during the study: changes in WHO ordinal scale, ICU admission/discharge date, mechanical ventilation start/end date, admission/discharge date, all-cause mortality at 4 weeks
- The receipt of additional anti-inflammatory treatments such as tocilizumab will be recorded within 14 days
- Vital signs will be recorded during 14 days until discharge to determine the time to defervescence and clinical improvement
- For the analysis of virological clearance of SARS-CoV-2, samples from the upper or lower respiratory tract will be collected at baseline (if not already performed on admission) to confirm SARS-CoV-2 infection and again on day 4-7 and day 14/discharge (only when discharged on day 10-13). Subsequently, samples will be analysed at the central laboratory of the study site using a quantitative assay according to validated standard in-house procedures. A negative result will be confirmed by a second test at least 12 hours apart.
- For the analysis in changes of biomarker levels CRP- LDH, D-dimer, IL-6 and lymphocytes will be measured in blood samples collected on day 0, 1-3 and every second day afterwards until day 14 or discharge. Blood samples will be sent to and analysed by validated methods in the central laboratory of respective study sites according to standard in-house procedures
- The incidence of acute kidney injury will be evaluated according to the KDIGO classification. Baseline creatinine will be defined as a concentration obtained within a 12-month period before admission and considered to be representative of the baseline kidney function according to the judgment of the treating physician. If this reference value is not available, the minimum of either serum creatinine at the time of admission or study inclusion, or in patients without chronic kidney disease, a calculated serum creatinine concentration using the MDRD equation will be used.
- For the analysis of inflammatory proteins, parameters of the contact activation and coagulation system and cytokines, blood samples will be collected on day 0, 1, 3, 5, 7, 10 and day 14 or discharge (in Basel, optional for other centers). Blood samples will be sent to the central laboratory of the University Hospital Basel and the other centers, respectively, centrifuged, aliquoted and stored at -80°C. Subsequently, samples will be analysed in duplicate in batches by commercially available, validated ELISAs in the Clinical Immunology Laboratory ([name]) and the Immunology division of the central laboratory by

a blinded technician. Blank and zero sample and three quality control samples (low, medium and high concentration) in duplicate will be included in each run. Accuracy values of the quality control samples should be within +/- 15% of the nominal values (or study samples will be re-analysed). In addition, all samples from the same participant will be analysed together in the same analytical run.

- For the analysis of conestat alfa pharmacokinetics (C1INH activity and concentration), blood samples will be collected at baseline, 5-10 minutes after the first administration and again immediately before and 5-10 minutes after a subsequent administration on day 1 (in Basel, optional for other centers). Blood samples will be sent to and analysed by validated methods in the central laboratory of the University Hospital Basel according to standard in-house procedures. Samples from other centers will be stored at -80°C before being shipped to and analysed in Basel.
- For the analysis of renal injury markers, urine samples will be collected at baseline, day 1, 3, 5, 7, 10 and day 14 or discharge (in Basel, optional for other centers). Samples will be centrifuged, aliquoted and stored at -80°C. Subsequently, all samples will be analysed in duplicate in batched by commercially available, validated ELISAs in the Clinical Immunology Laboratory ([name]) in Basel.

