5.3 Other Outcomes of Interest

- Changes in the ordinal WHO scale from baseline over 14 days
- Length of hospital stay until day 28 in survivors.
- Proportion of participants progressing to mechanical ventilation on day 7 and day 14
- Proportion of participants requiring ICU treatment on day 7 and 14
- Length of ICU stay until day 28
- Ventilator-free days until day 28
- All-cause mortality (time from randomisation to death within four weeks)
- Changes in biomarker levels until day 14: CRP, LDH, D-dimer, ferritin, IL-6, lymphocyte count
- Time to virological clearance of SARS-CoV-2 by PCR from upper or lower respiratory tract samples (time from enrolment to first of 2 negative assays at least 12 hours apart)
- Proportion of patients receiving additional anti-inflammatory treatment such as tocilizumab or immunoglobulins within 14 days
- Time to defervescence (temperature <38.0°C sustained for at least 48 hours)
- Time to clinical improvement (defervescence, normalization of oxygen saturation (>93%) and respiratory rate) until day 28
- Duration of supplemental oxygen until day 28
- Incidence of acute kidney injury classified on the basis of the worst serum creatinine according to the KDIGO classification, and changes of serum creatinine and estimated glomerular filtration rate (eGFR, estimated with the CKD-EPI equation) from baseline
- In a subgroup of patients (in Basel and optional in other centers) the pharmacokinetics and pharmacodynamics of conestat alfa in COVID-19 patients will be characterized by measuring the concentration of conestat alfa and the activity of C1INH, inflammatory cytokines and proteins (such as C4d, C5a, sC5-b9, IL-10) and parameters of the contact activation and coagulation cascade (such as factor XII and pre-kallikrein). In addition, changes of urinary markers of renal injury (such as NGAL, KIM-1, osteopontin and clusterin) from baseline will be analysed.

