9.2.4.3 Vital signs

No study specific vital signs will be assessed. All patients will be monitored regarding blood pressure, heart rate, respiratory rate and oxygen saturation as per standard operating procedures for the treatment of COVID-19 patients.

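### Two exploratory outcomes run to day 28 and defervescence needs 48 hours, but vital signs and oxygen need are scheduled only to day 14 or discharge

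*Protocol*

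**What the plan says.** Section 5.3 of the protocol lists three outcomes that depend on daily bedside data:

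- "Time to clinical improvement (defervescence, normalization of oxygen saturation (>93%) and respiratory rate) until day 28"
- "Duration of supplemental oxygen until day 28"
- "Time to defervescence (temperature <38.0°C sustained for at least 48 hours"; this item carries no day-28 limit of its own.

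Section 9.2.3 names the data source for the first and third: "Vital signs will be recorded during 14 days until discharge to determine the time to defervescence and clinical improvement". The schedule in 9.1 agrees. It marks vital signs on days 0, 1 and 2, on days 3 to 13 while admitted, and at day 14 or discharge, but not at week 4. Its footnote has the worst value of each day documented. Section 9.2.4.3 adds "No study specific vital signs will be assessed", so no measurement at home is foreseen.

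Oxygen need appears in 9.3.1 as "Assessment of WHO ordinal scale and need for oxygen supplementation", from Visit 2 through Visit 6. Visit 7 at week 4 asks instead for "Assessment of adverse events, WHO ordinal scale, admission to ICU and/or mechanical ventilation by structured telephone interview", with a back-up: "If necessary, medical charts will be reviewed, discharge summaries will be obtained".

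The synopsis (Statistical Considerations) plans Kaplan-Meier plots and a logrank test for time to defervescence. Section 11.4.3 treats all other outcomes of interest as descriptive and exploratory.

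**The concern.** An outcome with a 28-day horizon needs data over 28 days, or a rule that makes later data unnecessary. Here the sentence that names the data source stops at half the horizon, or sooner if the patient goes home. This is a matter of collection rather than analysis: an analysis plan can decide how to treat a missing day, but it cannot supply a temperature, saturation or respiratory rate that nobody was asked to record.

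The 48-hour requirement raises a second problem. Recording ends at discharge, and discharge usually follows recovery. A patient who becomes afebrile and leaves within 48 hours has probably met the clinical meaning of the outcome but cannot be shown to have met its definition. If that patient is censored at discharge, the logrank test treats the censoring as unrelated to prognosis, although it marks a good course. Vital-sign clinical improvement includes defervescence and inherits the problem.

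At stake is what these exploratory outcomes can validly describe, not the main conclusion of the trial.

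**Working it through.** The protocol gives no figure to reproduce, so the check sets the outcome windows against the recording windows.

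**1. Vital-sign clinical improvement.** The outcome horizon is day 28 (5.3). The last planned vital signs are at day 14 or discharge (9.2.3, 9.1). For a patient still in hospital at Visit 6:

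- Visit 6 on day 14: (28 − 14)/28 = 50% of the horizon has no planned vital signs.
- Visit 6 on day 16: (28 − 16)/28 = 43%.
- Visit 6 on day 12: (28 − 12)/28 = 57%.

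A patient discharged on an earlier day D has no planned vital signs from D onward. The only contacts after discharge are a telephone call for the ordinal scale if discharge came before day 7, and the week-4 interview. Outpatient scores 1 and 2 describe limitation of activities and say nothing about temperature, saturation or breathing rate.

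**2. Duration of supplemental oxygen.** The horizon is again day 28. The last scheduled item is at Visit 6. By patient type:

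- Off oxygen before discharge and before Visit 6: the stop date falls inside the recorded period, so this stretch of oxygen is fully known.
- Still an inpatient on oxygen at Visit 6: Visit 7 gives one ordinal score. For an inpatient, score 3 against score 4 separates no oxygen from oxygen by mask or prongs. That is status on one day, not a stop date. Chart review may supply the date.
- Sent home on oxygen: scores 1 and 2 do not register it, and no interview item asks about it.

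Section 9.2.3 lists start and end dates for mechanical ventilation and dates for ICU stay, but none for oxygen.

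**3. Defervescence.** Temperatures are documented as a daily worst value, so 48 hours corresponds to about two days. With discharge on day D, the 48 hours can be confirmed in hospital only if the fever ended by about day D − 2:

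| Discharge day | Latest confirmable end of fever |
|---|---|
| 3 | day 1 |
| 5 | day 3 |
| 7 | day 5 |
| 10 | day 8 |
| 14 | day 12 |

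For an active-arm patient who receives all doses, section 8.2.1 puts the last dose 64 hours after the first and keeps the patient in hospital at least 12 hours more: 64 + 12 = 76 hours. A fever that ends within 76 − 48 = 28 hours of the first dose is therefore confirmable even at the earliest planned discharge. A fever that ends later, followed by discharge within 48 hours, is not.

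The share of patients in that last group cannot be computed from the protocol. It needs the joint distribution of end of fever and discharge, and neither is given.

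**The case against.** The strongest reply is that much of this belongs to the analysis plan. No section says that discharge censors defervescence; the synopsis names only the method. Whether discharge is an event, a censoring time or a competing event is ordinary analysis-plan content, so its absence here is not an error. That stands, and the remark about informative censoring is accordingly conditional. It does not answer the collection gap.

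A second reply is that hospital charts are source data and may be reviewed at week 4. This helps for inpatients beyond day 14, mainly with oxygen dates. It does not help after discharge, and it is optional, whereas 9.2.3 fixes a recording window that ends earlier.

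Some stronger readings are tempting and should be resisted:

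- A reader might infer that early-discharged responders cannot reach defervescence at all. Only those who leave within 48 hours of becoming afebrile are affected. Entry also requires an expected stay of three calendar days.
- A reader might infer bias against conestat alfa, because a working drug would shorten stays. The protocol does not support a sign. Early end of fever is fully observed. The 12-hour stay after the last dose is written for treated patients with no counterpart for controls, which could favour confirmation in the active arm. Fever is not required for entry, so the number at risk is unknown.
- A reader might gauge the loss by assuming a length-of-stay distribution and counting patients still admitted on day 7 or 14. That does not measure lost events: a patient who has already had the event needs no further coverage.
- A reader might conclude that nothing about oxygen is known for half the horizon. That is wrong for every patient who stopped oxygen before discharge.

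**Conclusion.** The mismatch is real and minor. Sections 5.3, 9.2.3 and 9.3.1 do not fit together. Vital-sign clinical improvement cannot be observed from planned data beyond day 14 or discharge, and the true horizon is therefore at most half the stated one, give or take the Visit 6 window. Oxygen duration has a narrower gap: patients still on oxygen at day 14, partly recoverable from charts, and patients discharged on oxygen. Defervescence cannot be confirmed for a subset of unknown size, and censoring that subset would be informative.

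The conclusion rests on reading the visit lists and schedule as the complete set of planned collections. It does not rest on any assumed length of stay, and it makes no claim about which arm would gain. The primary endpoint and the ordered secondary endpoints use other data. In particular, the secondary time to clinical improvement in 5.2 is a different outcome: it uses the ordinal scale, ends at day 14 and already counts live discharge.

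**What to change.** 1. In 5.3, end vital-sign clinical improvement at day 14, to match 9.2.3. An oxygen question at week 4 would not repair this outcome, because it supplies no temperature, saturation or respiratory rate.
2. For oxygen duration, either end it at day 14 as well, or keep day 28 and add the oxygen stop date, including home oxygen, to the Visit 7 interview.
3. For the analysis, in the protocol or the analysis plan: count live discharge with the last recorded temperature below 38.0°C as defervescence, dated to the first afebrile day, instead of censoring it. Treat death as never reaching the event within the horizon.

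The cost is a few words in 5.3 and 9.2.3 and, if day 28 is kept for oxygen, one interview question. The downside of the third step is that a relapse of fever at home within 48 hours of becoming afebrile would be missed; this should be acknowledged when the outcome is reported.
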